#### 8.5.4.5 MRSE

The measured MRSE, adjusted MRSE (to account for the measured distance of 4 meters) and change in MRSE from Postop Week 3 will be summarized by the descriptive statistics for continuous outcomes (such as mean and standard deviation) and the 95% confidence interval of the mean at each visit for implanted primary eyes and implanted fellow eyes of the LAL group and of the Control group. The descriptive statistics will also be stratified by the MRSE at Postop Week 3 with bins of  $\leq -3.00$  D,  $> -3.00$  D to  $-2.00$  D,  $> -2.00$  D to  $-1.00$  D,  $> -1.00$  D to  $< 1.00$  D,  $\geq 1.00$  to  $< 2.00$  D,  $\geq 2.00$  to  $< 3.00$  D, and  $\geq 3.00$  D for the two lens groups separately.

#### 8.5.4.6 Accuracy of MRSE

The number and percent of eyes with a MRSE correction compared to the intended target within 0.25 D, 0.50 D, 0.75 D, 1.0 D, 1.25 D, 1.5 D, 1.75 D, and  $\geq 2.0$  D at each visit will be reported by eyes and lens group, at Postop Month 3 and Postop Month 6. For LAL eyes, the targeted post-adjustment MRSE is 0.00 D in all cases. The attempted MRSE adjustment is the Postop Week 3 MRSE in the primary analysis and will be the highest absolute MRSE at any of the adjustment visits in a supportive analysis. For Control eyes, the targeted post-adjustment MRSE is the Postop Week 3 MRSE and the attempted MRSE adjustment is 0. Additionally, the deviation of the achieved adjustment from the attempted adjustment will be summarized by the descriptive statistics for continuous outcomes. For the LAL group, the descriptive statistics will also be stratified by the MRSE at Postop Week 3 with bins of approximately 1.00 D wide.

The 95% confidence interval of the mean deviation and the 95% confidence interval of the proportion of eyes within 0.50 D and 1.00 D will be provided.

To evaluate any potential bias introduced by poor IOL power selection in the control arm, descriptive statistics of the difference in magnitude of MRSE measured at the Postop Week 3 visit will be calculated. 95% confidence intervals on the mean difference will be calculated.

#### 8.5.4.7 Absolute MRSE

The analyses methods described for the MRSE will be used for analyzing the absolute MRSE.

#### 8.5.4.8 Refractive MRSE stability

The refractive stable point will be determined based on the criteria described in Section F.3 of ANSI Z80.11-2012 document as follows:

- At least 95% of the treated eyes have a change  $\leq 1.00$  D of MRSE between the two refractions;
- The mean rate of change in MRSE, as determined by a paired analysis, is  $\leq 0.5$  D per year (0.04 D/month) over the same time period;
- The mean rate of change of MRSE decreases monotonically over time, with a projected asymptote of zero or a rate of change attributable to normal aging;
- The 95% confidence interval for mean rate of change includes zero or a rate of change attributable to normal aging.

The MRSE change between Postop Month 3 and Postop Month 6 will also be presented by eye and lens group.

#### 8.5.4.9 Defocus Equivalent (DEQ)

The DEQ, as defined as the absolute value of the MRSE error to target plus half the absolute value of the MRCYL, will be summarized descriptively by eye and lens group at Postop

Week 3, Postop Month 3, and Postop Month 6 visits. The number and percent of eyes with DEQ  $\leq 0.5$  D and 1.0 D will also be summarized at the corresponding visit.

#### 8.5.4.10 Autorefraction

Autorefraction sphere, cylinder, and spherical equivalent will be summarized descriptively at each visit by eye and lens group. Additionally, the vector analysis based on an IRC of MRCYL at Postop Week 3 and SIRC based on autorefraction cylinder (ARCYL) at Postop Month 6 will be performed by eye and lens group.

#### 8.5.4.11 Monocular Visual Acuity

The study includes the following monocular visual acuities:

- Distance Visual Acuity
  - Monocular photopic uncorrected distance visual acuity (no trial lens in front of eye)
  - Monocular photopic uncorrected distance visual acuity (monocular photopic UCDVA) using a +0.25 D lens to compensate for 4 meter test distance
  - Monocular photopic best distance corrected visual acuity (monocular photopic BCVDA)
- Intermediate Visual Acuity
  - Monocular photopic uncorrected intermediate visual acuity (monocular photopic UCIVA)
  - Monocular mesopic distance corrected intermediate visual acuity (monocular mesopic DCIVA)
  - Monocular photopic distance corrected intermediate visual acuity (monocular photopic DCIVA)
  - Monocular mesopic best corrected intermediate visual acuity (monocular mesopic BCIVA)
- Near Visual Acuity
  - Monocular photopic uncorrected near visual acuity (monocular photopic UCNVA)
  - Monocular mesopic distance corrected near visual acuity (monocular mesopic DCNVA)
  - Monocular photopic distance corrected near visual acuity (monocular photopic DCNVA)
  - Monocular mesopic best corrected near visual acuity (monocular mesopic BCNVA)

For each of the above monocular visual acuities, the outcomes will be presented with the number and percent of eyes that fall into each VA category at each visit (e.g. 0.00 logMAR or better, 0.10 logMAR or better, 0.20 logMAR or better, etc.) by eye (primary eyes and fellow eyes) and lens group (LAL versus Control). The logMAR values will be summarized by descriptive statistics for continuous outcomes for each visit by eye and lens group. Odd ratios, comparing LAL versus Control primary eyes and their confidence intervals will be presented for the odds of UCDVA with a +0.25 D lens being worse than logMAR 0.00, 0.10,

0.20, and 0.30. Change in visual acuity from the Postop Week 3 visit will be presented at each visit as categorical outcomes of “increase of 15 letters or more”, “Increase of 10-14 letters”, “Increase of 5-9 letters”, “No change”, “Decrease of 5-9 letters”, “Decrease of 10-14 letters”, and “Decrease of 15 letters or more” by eye and lens group. The change in logMAR values from the Postop Week 3 visit will also be presented by eye and lens group. A subgroup analysis will be performed based on the amount of refractive error present at the Postop Week 3 visit. A comparison of the mean difference between the LAL and Control for these subgroups will be presented.

For the postoperative 6-Month DCIVA (both mesopic and photopic) and DCNVA (both mesopic and photopic), the mean logMAR values will be stratified by the MRSE at Postop Week 3 with bins of  $\leq -3.00$  D,  $> -3.00$  D to  $-2.00$  D,  $> -2.00$  D to  $-1.00$  D,  $> -1.00$  D to  $< 1.00$  D,  $\geq 1.00$  to  $< 2.00$  D,  $\geq 2.00$  to  $< 3.00$  D, and  $\geq 3.00$  D for the LAL eyes.

In order to address the effect of pupil size, the analyses for the mesopic visual acuity described above will be stratified by the mesopic pupil size ( $< 3.0$  mm,  $\geq 3.0$  to  $\leq 4.0$  mm, and  $> 4.0$  mm). In order to assess the effect of the distance refractive error on the uncorrected acuity, a scatter plot with Postop Month 6 logMAR UCDVA using a +0.25 D lens as the Y-axis and Postop Month 6 MRSE as the X-axis will be prepared. The Regression Analysis with a regression model using logMAR UCDVA using a +0.25 D lens at Postoperative Month 6 as the dependent variable and the corresponding MRSE as the independent variable will be performed. The effect of the MRCYL and that of DEQ on the logMAR UCDVA using a +0.25 D lens will also be analyzed based on the same regression analysis. The scatter plot and the regression analysis will also be performed for the Postop Month 6 logMAR UCIVA and UCNVA.

It should be noted that the change in monocular photopic BCDVA are treated as key safety outcomes and the associated analyses are described in Section 8.6.2 below.

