The principal investigator or delegated MD Sub-Investigator will review the Inclusion/Exclusion checklist document provided for the study and, if the subject is eligible, sign and date the form. The documentation of eligibility must be completed prior to implantation. Subjects that meet all inclusion/exclusion criteria will be randomly assigned in a 1:1 ratio to either the LAL group or the Control group. In addition, each eye of the subject will be assigned as either the primary eye or the fellow eye based on randomization. Pre-determined randomization schemes will be utilized. A randomization schedule for the treatment assignments (LAL versus Control) with a block of 4 and a ratio of 1:1 will be generated using a random generator such as SAS. Randomization of subjects will occur immediately prior to commencing cataract surgery on the primary eye. Only subjects meeting all inclusion/exclusion criteria may be implanted. Those subjects who do not meet the inclusion/exclusion requirements will be considered screen failures. Exit forms will be completed for all screen fails. Up to 350 subjects may be enrolled to allow for up to 230 subjects who will have had implantation of the LAL IOL or Control IOL attempted in the FAS. An additional 17 subjects were implanted in the pre-COVID-19 population.

The implant lens powers for the LAL and Control IOLs will be calculated based upon ocular biometry data and a lens power formula of the investigator's choice. Optimized lens constants of the investigator's choice also may be utilized. These lens constants will not be changed during the clinical investigation. For all study eyes, a postoperative spherical equivalent (SE) outcome closest to emmetropia as measured on a 4 meter exam lane will be targeted. The lens power will not be altered based on intraoperative diagnostics.

Subjects randomized to the LAL group

Commencing at the Postop Week 3 [REDACTED] visit (17-24 days post-Fellow eye operative visit), both eyes will receive an [REDACTED]  
[REDACTED]

At the Adjustment #1 visit (3-7 days after the Postop Week 3 [REDACTED] visit), both eyes will receive an adjustment #1 light treatment based on the measured manifest refraction at 4 meters at this visit. Eyes measured with a manifest cylinder of  $\geq 0.50$  D will receive a spherocylindrical light treatment while eyes with  $< 0.50$  D of manifest cylinder will receive a non-astigmatic light treatment.

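### A single slope of uncorrected distance acuity on signed MRSE understates the effect of refractive error and, at the planned target, points the wrong way for hyperopic eyes

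*Combined protocol and SAP*

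**What the plan says.** The purpose given in section 8.5.4.11 is "In order to assess the effect of the distance refractive error on the uncorrected acuity". The plan asks for a scatter plot of Month 6 logMAR UCDVA (with the +0.25 D lens) against Month 6 MRSE, then a regression with that acuity "as the dependent variable and the corresponding MRSE as the independent variable will be performed". No functional form is stated, and the text does not say whether measured or adjusted MRSE is meant, or whether the lens groups are fitted separately.

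Four other places bear on this:

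- Section 8.5.4.5 derives both a measured MRSE and an "adjusted MRSE (to account for the measured distance of 4 meters".
- Section 8.5.4.7 treats the unsigned quantity as a separate variable: "The analyses methods described for the MRSE will be used for analyzing the absolute MRSE". Plain MRSE is therefore signed, as the bins in 8.5.4.5 (from -3.00 D or below to +3.00 D or above) confirm.
- Section 7.2 sets the surgical aim for all study eyes: an "outcome closest to emmetropia as measured on a 4 meter exam lane will be targeted". Section 8.5.4.6 puts the post-adjustment target for LAL eyes at 0.00 D.
- The same paragraph of 8.5.4.11 adds "The effect of the MRCYL and that of DEQ on the logMAR UCDVA using a +0.25 D lens will also be analyzed". Section 8.5.4.9 gives the definition: "The DEQ, as defined as the absolute value of the MRSE error to target plus half the absolute value of the MRCYL".

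The regression is repeated for uncorrected intermediate and near acuity.

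**The concern.** A pseudophakic eye that is out of focus for distance loses acuity whether the error is myopic or hyperopic. Plotted against signed MRSE, logMAR falls to a minimum at best focus and rises again. One slope through that shape is a weighted average of a downward and an upward limb. Its size and sign then depend on where the eyes happen to centre, and it understates how strongly refractive error drives acuity.

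UCDVA with the +0.25 D lens is the fifth secondary endpoint, and light adjustment is meant to reduce residual refractive error. This regression is one of the few visible places where the plan examines how far residual refraction explains uncorrected acuity. A weak or one-directional slope could be read as saying that refractive accuracy matters less than it does.

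**Working it through.** The plan states no figure for this regression, so there is none to reproduce. It gives no MRSE distribution and no acuity loss per dioptre either; those values below are assumptions.

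**1. Best focus.** A chart at 4 m presents 1/4 = 0.25 D of vergence, which the +0.25 D lens cancels, so the eye must be focused at infinity. An eye whose refraction on the 4 m lane is +0.25 D is in that state. Best focus is therefore at measured MRSE +0.25 D, or zero on adjusted MRSE (taken as measured minus 0.25 D). With a straight line, choosing measured or adjusted MRSE moves only the intercept; the choice matters once the limbs are separated.

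**2. The single slope.** Suppose logMAR rises by k_m per dioptre on the myopic side and k_h on the hyperopic side, and MRSE is normal with mean m and standard deviation s. The least-squares slope on signed MRSE is the average local slope:

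slope = k_h × P(hyperopic) - k_m × P(myopic), where P(hyperopic) = 1 - Φ((0.25 - m)/s).

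**3. Eyes centred on the planned target.** Take m = 0, s = 0.4, k_m = k_h = 0.25, noise SD 0.08.

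- P(hyperopic) = 1 - Φ(0.625) = 0.27; P(myopic) = 0.73.
- Slope = 0.25 × (0.266 - 0.734) = -0.12 logMAR per dioptre, about half the true 0.25 in size and opposite in sign to the hyperopic limb.
- Distance from focus, |MRSE - 0.25|, has mean square 0.25² + 0.4² = 0.2225 and mean 0.3795, so its variance is 0.2225 - 0.1440 = 0.0785.
- Total logMAR variance = 0.25² × 0.0785 + 0.08² = 0.0049 + 0.0064 = 0.0113.
- R2, signed MRSE = (0.117² × 0.16)/0.0113 = 0.19.
- R2, two-slope fit = 0.0049/0.0113 = 0.43.

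With m still at 0, s from 0.3 to 0.5 D and k from 0.25 to 0.40, the same formulas give R2 of 0.17 to 0.35 for signed MRSE and 0.33 to 0.74 for the two-slope fit.

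**4. Where the slope vanishes.** With equal limbs it is zero only when P(hyperopic) = 0.5, that is, when eyes centre at +0.25 D. There R2 is 0.00 for signed MRSE against 0.36 for distance from focus (s = 0.4, k = 0.25), and with 112 eyes the slope is significant in about 14% of simulated trials. Centred at 0.00 D, with 0.30 logMAR per dioptre, s from 0.25 to 0.50 D and 90 or 112 eyes, it is significantly negative in 96% to 100%.

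**5. Unequal limbs.** Hyperopic error acts like negative-lens defocus, the direction in which the LAL is meant to gain depth of focus, so its hyperopic limb may be shallow. With k_h = 0.05, k_m = 0.25, m = 0 and s = 0.4, R2 is about 0.39 for signed MRSE, about the same for absolute adjusted MRSE, and 0.47 for two slopes. Taking the absolute value is therefore not enough.

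**6. DEQ as a safeguard.** DEQ is unsigned but is measured from target. Section 8.5.4.6 takes the Control target to be the eye's own Week 3 MRSE. On that definition Control DEQ is drift since Week 3 plus half the cylinder. Under the step 3 assumptions, with drift SD 0.15 to 0.25 D and mean cylinder about 0.35 D, its R2 for UCDVA is 0.00 to 0.02, or 0.04 to 0.06 if cylinder itself costs 0.10 logMAR per dioptre. If DEQ is instead measured from 0.00 D in every eye while best focus is at +0.25 D, it detects an effect in 78% to 100% of runs under the step 4 assumptions.

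**7. Intermediate and near acuity.** Best focus is at about -1/0.67 = -1.5 D and -1/0.40 = -2.5 D. Eyes aimed at zero lie almost all on one side, so signed MRSE is reasonable there.

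**The case against.** The strongest reply is that the paragraph contains more than this one regression. The scatter plot would show a two-sided pattern to anyone who looked, and DEQ is an unsigned measure of refractive error that properly includes cylinder. Much of this stands: read as a whole, the section is unlikely to conclude that refraction is irrelevant. It does not fully rescue the analysis. The plot does not correct the reported slope, and DEQ is a safe substitute only if its target is emmetropia in both groups, which the plan leaves open for Control eyes.

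A second reply is that the plan never says linear. That is correct. A straight line is the natural reading of one named independent variable, but it remains an inference. If another form is intended, it is unstated and still needs to be written down.

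A reader might infer more: that the analysis will report no effect of refractive error. The documents do not support this. With equal limbs, a near-null slope needs eyes centred near +0.25 D, whereas sections 7.2, 7.4 and 8.5.4.6 aim at emmetropia on the 4 m lane or at 0.00 D. Centred there, the slope is nearly always significant, and its direction is right for the roughly 73% of eyes on the myopic side.

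A reader might also infer that the fifth secondary endpoint is compromised. It is not. Section 8.5.4 is descriptive, and section 8.5.2 shows that the endpoint uses an ANCOVA whose covariates are not visible in the public text.

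**Conclusion.** The point holds with limited force. For UCDVA through the +0.25 D lens, a single slope on signed MRSE is a poor summary of a two-sided relation. At the planned centring it understates the effect and gives hyperopic eyes the wrong direction: slope -0.12 against limbs of 0.25 logMAR per dioptre, R2 0.19 against 0.43, about 27% of eyes on the hyperopic side. These sizes rest on the assumed spread, acuity slope and noise. The averaging of opposing limbs does not depend on those values; the location of best focus follows from the 4 m test distance and the stated lens. The DEQ regression is a partial safeguard whose value in Control eyes depends on a target the plan should settle. Severity is low, because no endpoint test, success rule or sample size depends on the result.

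**What to change.** In section 8.5.4.11, for UCDVA with the +0.25 D lens, replace the single MRSE term by adjusted MRSE with separate myopic and hyperopic slopes that meet at adjusted MRSE = 0, fitted by lens group. State that DEQ in this regression uses adjusted MRSE measured from emmetropia in both groups, whatever target section 8.5.4.6 uses for correction accuracy. Keep signed MRSE for UCIVA and UCNVA. Prefer two slopes to the absolute value, which would impose a symmetry that an extended-focus lens may not have.

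The cost is one or two sentences in the SAP and one extra parameter per group. No new data are needed. If few eyes lie on the hyperopic side in a group, that slope will be imprecise, and its confidence interval should be reported with it.

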#### **8.5.4.12 Binocular Visual Acuity**

The study includes the following binocular visual acuities:

- Binocular photopic uncorrected distance visual acuity (binocular photopic UCDVA) using a +0.25 D lens over each eye to compensate for 4 meter test distance
- Binocular photopic uncorrected intermediate visual acuity (binocular photopic UCIVA)
- Binocular photopic uncorrected near visual acuity (binocular photopic UCNVA)

The analyses methods described for the monocular uncorrected visual acuity will be performed for binocular visual acuity based on implanted subjects by lens group.

#### **8.5.4.13 Depth of Focus**

Descriptive statistics of the logMAR visual acuity measured at each lens diopter will be calculated for the depth of focus test performed at Postop Month 6 by eye and lens group.

The defocus curve and the estimated DOF will also be stratified by the photopic pupil size (<3.0 mm,  $\geq 3.0$  to  $\leq 4.0$  mm, and  $>4.0$  mm) and by the axial length measured preoperatively (<21.0 mm, 21.0 mm to  $\leq 26.0$  mm, and  $>26.0$  mm).

## 8.6 SAFETY PARAMETERS

The following safety outcomes will be summarized descriptively based on the observed data of the modified Safety population. The 95% confidence intervals for means or percentage may be presented, as appropriate. Key safety outcomes will also be provided for the Pre-COVID-19 population.

### 8.6.1 ADVERSE EVENTS (AE)

For each adverse event, the number of reports, number and percent of subjects with the AE, and number and percent of eyes with the AE will be summarized at the operative visit and each postoperative visit by lens group. Serious ocular AEs and the non-ocular serious AEs will be summarized in the same manner. Additionally, for each device-related AE reported during the study will be presented in the same manner.

Each ISO-defined cumulative and persistent adverse event at Postop Month 6 will be summarized using the count and percent of the subjects reported with such event along with the one-sided lower 95% confidence limit of the percent based on the binomial distribution. If the lower limit is below the ISO specified SPE rate for the respective AE, then it will be concluded that the LAL does not have a rate higher than the corresponding SPE rate specified by the ISO.

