### Safety Parameters:

#### *Primary Endpoint*

- Incidence of ocular serious adverse events including persistent and cumulative events defined per ISO 11979-7

The ISO-event rates for all subjects in the LAL group and Control group will be presented separately. Additionally the event rate of the LAL subjects will be compared to the “safety and performance endpoints (SPE)” rates specified in ISO.

The incidence of all other adverse events will also be presented separately for the LAL group and Control group. In addition, the incidence of secondary surgical intervention (SSI) related to the optical properties of the lens will be provided.

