#### **8.1.2 SAMPLE SIZE FOR THE SAFETY ENDPOINTS**

##### **Primary Safety Endpoint**

The sample size for the incidence of ocular serious adverse events, including persistent and cumulative events defined per ISO 11979-7, is based on the recommendation from American Academy of Ophthalmology Task Force Consensus Statement for Extended Depth of Focus Intraocular Lenses, “*The EDF IOL group should consist of a minimum of 100 patients.*” With 100 LAL subjects, the study has 95% confidence to observe at least one incidence of safety events with a rate of at least 2.7%. With a drop-out rate of 10%, at least **112** LAL subjects with implantation attempted are needed. For comparison, at least 112 Control subjects with implantation attempted are needed.

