### **8.2 GENERAL CONSIDERATION**

The statistical analysis of the data will be performed using SAS version 9.3 or higher or another industry standard statistical software package. Continuous variables will be summarized using descriptive statistics, specifically the mean, median, standard deviation, minimum and maximum. Categorical variables will be summarized by frequencies and percentages. For monocular measurements such as refraction or monocular visual acuity, the summaries will be provided for the primary eyes and fellow eyes of the LAL subjects and those of the Control subjects separately. For binocular measurements such as binocular visual acuity or the patient reported outcomes, the summaries will be provided for the LAL subjects and Control subjects separately. The 95% confidence interval for mean or for percentage may be provided.

Unless otherwise specified, all p-values will be two-sided for a two-sided significance level of 0.05 or one-sided for a one-sided significance level of 0.025. In general, the confidence intervals will be two-sided at 95% confidence level. For the ISO-specified cumulative or persistent adverse event rate, one-sided lower 95% confidence limit will be provided.

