#### **8.6.12 SECONDARY SURGICAL INTERVENTION (SSI)**

Rates of secondary surgical intervention (IOL exchange, removal, and repositioning) related to the optical properties of the IOL will be reported by lens group (LAL versus Control) in the modified Safety population. The two-sided 95% confidence intervals of these rates will be calculated as well as on the difference in rates. SSIs related to the optical properties of the IOL are defined as an SSI due to subject intolerance of visual symptoms not adequately improved by spectacle correction. All SSIs should include investigator assessment

determining if it is “related” or “not related” to the IOL optical properties.

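### The adverse event rule in 8.6.1 turns failure to show an excess over the ISO SPE rate into a conclusion that the LAL rate is not higher

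*Combined protocol and SAP*

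**What the plan says.** Sections 1.6 and 5.2 make the incidence of ocular serious adverse events, including the ISO 11979-7 cumulative and persistent events, the primary safety endpoint. They add that "the event rate of the LAL subjects will be compared to the" ISO SPE rates. The rule for this comparison is in 8.6.1. Each ISO event at Postop Month 6 is reported as a count and percent with a "one-sided lower 95% confidence limit of the percent based on the binomial distribution". Then: "If the lower limit is below the ISO specified SPE rate for the respective AE", "it will be concluded that the LAL does not have a rate higher than the corresponding SPE rate specified by the ISO".

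Section 8.2 repeats the choice of limit: "For the ISO-specified cumulative or persistent adverse event rate, one-sided lower 95% confidence limit will be provided". Neither section asks for an upper limit on these rates. Other intervals in the safety analyses are optional (8.6: "The 95% confidence intervals for means or percentage may be presented, as appropriate"). By contrast, 8.6.12 requires intervals for secondary surgical interventions related to the optical properties of the lens: "The two-sided 95% confidence intervals of these rates will be calculated as well as on the difference in rates".

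Section 8.1.2 takes the safety sample size from a recommendation of at least 100 patients in the extended depth of focus group, raised to 112 for 10% drop-out. It states that with 100 LAL subjects "the study has 95% confidence to observe at least one incidence of safety events with a rate of at least 2.7" percent. Power against the SPE rates is not considered.

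**The concern.** The comparison of the lower limit with the SPE rate is a one-sided 5% test of the hypothesis that the LAL rate is at or below the SPE rate. If the lower limit exceeds the SPE rate, the test rejects and an excess is shown. If it does not, the test has failed to reject, and the data may be compatible with rates well above the benchmark as well as below it. The plan treats this second outcome as positive evidence that the LAL rate is not higher.

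The consequence is that weaker evidence makes the favourable statement easier to obtain. Zero events always satisfies the rule, whatever the number of subjects. With few subjects, several times the benchmark rate can also satisfy it. This is the only readable inferential rule for the primary safety endpoint, so an unsupported statement could be carried into the report of a device trial as a pre-specified conclusion.

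**Working it through.** **Inputs.** From 8.1.2: 112 LAL subjects with implantation attempted, and 100 after 10% drop-out. From 8.6.1 and 8.2: one-sided lower 95% limit, binomial. The SPE rates are not in the documents, so I assume 0.5%, 1%, 2% and 3%.

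**The plan's own figures.** 100 / (1 − 0.10) = 111.1, rounded up to 112, as stated. The chance of at least one event at a true rate of 2.7% is 1 − (1 − 0.027)^n. This is 93.5% for n = 100 and 95.3% for n = 112. The quoted 2.7% therefore fits about 110 subjects; at n = 100 the rate detectable with 95% confidence is 2.95%. The gap is small and the argument does not rest on it.

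**What the rule accepts.** With x events in n subjects, the exact (Clopper-Pearson) one-sided 95% limits are:

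- lower: the 0.05 quantile of Beta(x, n − x + 1), and 0 when x = 0
- upper: the 0.95 quantile of Beta(x + 1, n − x)

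For each assumed SPE rate I took the largest x whose lower limit is below that rate. I then computed the upper limit at that x and the binomial probability of x or fewer events when the true rate is double the SPE rate. For n = 112:

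| Assumed SPE rate | Largest count still concluded 'not higher' | Observed rate | Multiple of SPE rate | Lower limit | Upper limit | Chance of 'not higher' at double the SPE rate |
|---|---|---|---|---|---|---|
| 0.5% | 2 | 1.8% | 3.6 | 0.32% | 5.5% | 90% |
| 1% | 3 | 2.7% | 2.7 | 0.73% | 6.8% | 81% |
| 2% | 5 | 4.5% | 2.2 | 1.78% | 9.2% | 71% |
| 3% | 7 | 6.3% | 2.1 | 2.97% | 11.4% | 64% |

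For n = 100 the largest counts are 2, 3, 5 and 6 (4.0, 3.0, 2.5 and 2.0 times the SPE rate), and the chances at double the SPE rate are 92%, 86%, 79% and 61%. At triple the SPE rate with n = 112, the rule still concludes 'not higher' with probability 76%, 57%, 33% and 20%.

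**The flag itself.** When the true rate equals the SPE rate, the chance of flagging an excess at n = 112 is 1.9%, 2.7%, 2.5% and 2.0%, within the nominal 5% per event category.

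**What 'not higher' would need.** The upper limit must lie below the SPE rate. The best possible result is zero events, for which the upper limit is 1 − 0.05^(1/n):

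- n = 112: 1 − 0.05^(1/112) = 2.64%
- n = 100: 1 − 0.05^(1/100) = 2.95%

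For any SPE rate at or below these values, no result of this trial supports the statement, yet the rule grants it. At 3% and n = 112, only zero events would support it. The number of subjects needed with zero events is ln(0.05) / ln(1 − SPE), rounded up: 299 for 1% and 598 for 0.5%.

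**Less information helps.** At an assumed SPE rate of 1% and a true rate of 3%, the rule concludes 'not higher' with probability 31% for 230 subjects, 57% for 112 and 81% for 50.

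**The case against.** The strongest reply is that the test is right and only the wording is loose. Section 2.1 uses the ISO comparison to detect an excess: it reports that secondary surgical interventions in the earlier trial were significantly above the historical rate. Read that way, the sentence in 8.6.1 is shorthand for 'not significantly higher'. That explains how the sentence may have arisen, but a pre-specified conclusion has to be correct as written.

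Several points on weight do stand:

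- No readable section makes study success depend on the rule, and 8.6 describes these outcomes as descriptive.
- Text after the SPE sentence in 5.2 is redacted, so another criterion may exist there. The concluding sentence in 8.6.1 is complete and would still need correction.
- Section 8.1.2 provides at least 112 Control subjects for comparison, and rates are shown by lens group. Readers would see concurrent Control rates beside the statement, although no formal between-group test of these events is visible.
- Counts and percents are reported, so a reader could compute an upper limit.
- The multiples and probabilities depend on assumed SPE rates, and the largest multiple rests on two events.
- Low power follows from the sample size and remains after any rewording.

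It can also be said that a condition on the upper limit would hardly ever be met here. That is true, and it shows how little a trial of this size can say in favour of 'not higher' for rare events.

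**Conclusion.** The concern holds. The concluding sentence of 8.6.1 makes an affirmative statement that its own criterion cannot support, on the primary safety endpoint, and no readable section requires the upper limit that could support it. The logical point does not depend on the SPE rates. Its size does: for assumed rates of 0.5% to 3% and 100 or 112 LAL subjects, the rule accepts observed rates of about 2 to 4 times the benchmark, and it concludes 'not higher' in 61% to 92% of trials when the true rate is double the benchmark. These figures use exact binomial limits and treat each event category separately. The fault lies in the conclusion; the flag for an excess is valid. It should be fixed, but no visible success criterion turns on it.

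**What to change.** Keep the one-sided lower 95% limit as the flag and replace the last sentence of 8.6.1 with wording such as:

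> If the one-sided lower 95% limit exceeds the SPE rate, the LAL rate is significantly higher than the SPE rate. Otherwise the LAL rate is not shown to be higher, and the one-sided upper 95% limit is reported as the largest rate the data do not exclude. The LAL rate is stated to be not higher than the SPE rate only if that upper limit is below it.

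Add the one-sided upper 95% limit to the last sentence of 8.2. Do not take the lower limit from a two-sided 95% interval. That would move the flag from one-sided 5% to 2.5%, and at n = 112 the largest unflagged count would rise from 3 to 4 for an SPE rate of 1% and from 5 to 6 for 2%.

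The cost is two or three sentences and one more column in the adverse event table. Data, sample size and the excess flag do not change. The safety statement becomes less favourable: with 112 subjects, 'not higher' could be stated only for SPE rates above 2.64%, and at 3% only with zero events.
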